1.0 OBJECTIVES

Primary objective:

1. Determine the response rate (2008 IWCLL/NCI-WG criteria) to treatment with single-agent ofatumumab in previously untreated, early-stage, high-risk patients with CLL/SLL.

Secondary objectives:

1. Determine the time-to-progression for high-risk patients treated with ofatumumab.
2. Determine the time-to-next chemoimmunotherapy or alternative therapy.
3. Evaluate the pharmacokinetics of single-agent ofatumumab in high-risk, previously untreated patients with CLL/SLL.
4. Evaluate for circulating CD20⁺ cells through treatment and in follow-up in high-risk patients treated with ofatumumab.
5. Evaluate safety and toxicities of ofatumumab in previously untreated high-risk patients with CLL/SLL.

2.0 BACKGROUND

Rationale

Ofatumumab has significant single-agent activity in treating patients with CLL refractory to fludarabine and alemtuzumab (FA-ref) and fludarabine-refractory patients with bulky (>5cm) lymph nodes (BF-ref), as demonstrated by the interim analysis of the pivotal trial¹. The overall response rate (ORR) for FA-ref (n=59) and BF-ref (n=79) was 58% and 47%, respectively. The median duration of response (median) for both populations was approximately 6 months. Treatment with ofatumumab was very well tolerated. This fully human monoclonal antibody against CD20 binds to a unique epitope composed of the small- and large-loop domains and is highly effective at fixing complement for complement-dependent cytotoxicity (CDC). *In vitro* studies demonstrated higher levels of CDC against primary CLL cells and cell lines with ofatumumab compared to rituximab^{2,3}. In addition, a phase I/II trial of single-agent ofatumumab in relapsed patients with CLL demonstrated an ORR of 50% in the 26 patients treated with ofatumumab 500 mg followed by 3 weekly doses of 2000 mg (4 total doses). This treatment was well tolerated with the most common side effect being infusion-related reactions⁴.

Ofatumumab was combined with fludarabine (F) and cyclophosphamide (C) (O-FC) in a multi-center, Phase II randomized trial of 2-dose levels ofatumumab (500 versus 1000 mg) for treatment of previously untreated patients with CLL⁵. First course ofatumumab was 300 mg in both dose cohorts and both cohorts received F 25 mg/m² and C 250 mg/m², both daily for 3 days of each 4-wk course. There were 31 patients and 30 patients randomized to the 500 and 1000mg cohorts, respectively. This chemoimmunotherapy regimen was active and well tolerated. There were no statistically significant differences in efficacy or safety parameters between the dose cohorts. The CR rate for the 500 and 1000 mg cohorts was 32 and 50%, respectively; the ORR for the 500 and 1000 mg cohorts was 77 and 73%,

respectively. There were no ofatumumab infusion-related reactions \geq grade 3. Myelosuppression was the most frequent adverse event with O-FC regimen. This is a promising chemoimmunotherapy regimen and merits further study in frontline and previously treated patients with CLL.

Prior clinical trials demonstrated activity for rituximab in treating early-stage, treatment-naïve high-risk (β 2M \geq 3 mg/L) CLL⁶. The treatment was 8 weekly doses of rituximab 375mg/m². Patients were previously untreated, high-risk by elevated β 2M (\geq 3 mg/L). There were 34 patients enrolled and treated. The CR rate was 9%, nPR was 21%, and PR was 53% (ORR 82%). The median time to treatment failure (N=34) was 27 months and the median time to progression for responders (N=28) was 43 months. Responses and response duration will be compared to this historical trial. Time to first chemoimmunotherapy will be evaluated based on observed versus expected (O/E) ratio using the MDACC CLL database and multivariable models with nomograms developed to predict time to chemoimmunotherapy based in presenting characteristics. Given the activity and tolerability of ofatumumab, it is an ideal candidate to evaluate for single-agent activity in early-stage, high-risk patients with CLL.

The overall objective of this phase II study is to evaluate the efficacy of ofatumumab in treating high-risk, watch-and-wait, treatment-naïve patients with CLL/SLL to delay time to first chemoimmunotherapy treatment. For this clinical trial, patients will be defined as high-risk for progression based on the presence of one of the following: Rai stage II, serum beta-2 microglobulin (β 2M) of \geq 3 mg/L, absolute lymphocyte count \geq 25,000/ μ L, unmutated (\leq 2%) *IGHV* gene or mutated *IGHV3-21*, ZAP70 positive, CD38 positive (\geq 30%), or 11q or 17p deletion by FISH.

3.0 BACKGROUND DRUG INFORMATION

Ofatumumab FDA-Labeled Indication: refractory chronic lymphoid leukemia

Ofatumumab is currently under development by GlaxoSmithKline for the treatment of relapsed or refractory B-cell follicular lymphoma (FL) for previously untreated FL, for the treatment of relapsed or refractory B-cell chronic lymphocytic leukemia (CLL), for previously untreated CLL and for the treatment of active rheumatoid arthritis and other related autoimmune diseases.

US Trade Name: Arzerra

Dosing & Indications

How Supplied: Intravenous solution, 20 mg/mL

Adult Single-Agent Dosing

- Refractory chronic lymphoid leukemia: 300 mg IV, followed 1 week later by 2000 mg IV weekly for 7 doses (dose 2 to 8), followed 4 weeks later by 2000 mg every 4 weeks for 4 doses (dose 9 to 12); premedicate 30 min to 2 hr

before each dose with acetaminophen (1000 mg or equivalent), oral or IV antihistamine (cetirizine 10 mg or equivalent), and IV corticosteroid (prednisolone 100 mg or equivalent).

- Corticosteroid premedication dose may be gradually reduced for doses 3 through 8, if grade 3 or greater infusion reaction did not occur with the preceding dose.
- Corticosteroid premedication dose may be reduced to prednisolone 50 to 100 mg or equivalent for doses 10 through 12, if grade 3 or greater infusion reaction did not occur with dose 9.
- Initiate dose 1 at an initial rate of 12 mL/hr (3.6 mg/hr), if infusion is well-tolerated, rate may be escalated in 2-fold increments at 30 min intervals to a maximum of 200 mL/hr.
- Initiate dose 2 at an initial rate of 12 mL/hr (24 mg/hr), if infusion is well-tolerated, rate may be escalated in 2-fold increments at 30 min intervals to a maximum of 200 mL/hr
- Initiate (dose 3 through 12) at an initial rate of 25 mL/hr (50 mg/hr), if infusion is well-tolerated, rate may be escalated in 2-fold increments at 30 min intervals to a maximum of 400 mL/hr

Mechanism of Action/Pharmacokinetics

Mechanism of Action

Ofatumumab is a human IgG1-kappa monoclonal antibody that binds to the CD20 molecule on normal B lymphocytes and on B-cell chronic lymphocytic leukemia, resulting in B-cell lysis.

Pharmacokinetics (single-agent in refractory CLL)

- Distribution: 1.7 to 5.1 L
- Excretion: total body clearance, mean: 0.01 L/hr
- Elimination half life: approximately 14 days

Administration/Monitoring

Administration

Intravenous

- Do NOT shake, mix by gentle inversion.
- Do NOT mix ofatumumab with other drugs.
- Colorless solution with small amounts of visible, translucent-to-white, amorphous, ofatumumab particles is normal; do not use if discolored, cloudy, or if foreign particulate matter is present.
- Total volume of prepared solution should be 1000 mL; withdraw appropriate volume of 0.9% sodium chloride solution to accommodate volume of ofatumumab.
- Do NOT administer as an intravenous push or bolus.
- Do NOT administer ofatumumab with other drugs.
- Administer with an infusion pump, the in-line filter supplied with product, and polyvinyl chloride administration sets.

- Infusion should be started within 12 hr of preparation; discard prepared solution after 24.
- Initiate dose 1 at an initial rate of 12 mL/hr (3.6 mg/hr), if infusion is well-tolerated, rate may be escalated in 2-fold increments at 30 min intervals to a maximum of 200 mg/hr.
- Initiate dose 2 at an initial rate of 12 mL/hr (24 mg/hr), if infusion is well-tolerated, rate may be escalated in 2-fold increments at 30 min intervals to a maximum of 200 mg/hr.
- Initiate dose 3 through 12 at an initial rate of 25 mL/hr (50 mg/hr), if infusion is well-tolerated, rate may be escalated in 2-fold increments at 30 min intervals to a maximum of 400 mg/hr

Monitoring

- Evidence of tumor response is indicative of efficacy.
- CBC regularly, including platelet count and differential.
- CBC more frequently in patients who develop grade 3 or 4 cytopenias, including platelet count and differential.
- Hepatitis B virus (HBV) infection; clinical and laboratory screening before initiation of therapy for those at high risk of HBV infection; hepatitis B carriers, signs of active HBV for 6 to 12 months after therapy.
- Infusion reaction (bronchospasm, dyspnea, laryngeal edema, pulmonary edema, flushing, hypertension, hypotension, syncope, cardiac ischemia/infarction, back pain, abdominal pain, pyrexia, rash, urticaria, and angioedema), especially with first 2 infusions.

Dose Adjustments

- body weight: no dose adjustment is recommended
- gender: no dose adjustment is recommended
- infusion reaction, grade 1 or 2: interrupt infusion and if reaction resolves or remains less than or equal to grade 2, resume at one-half the previous infusion rate; resume infusion at normal infusion rate as tolerated
- infusion reaction, grade 3: interrupt infusion and if reaction resolves or remains less than or equal to grade 2, resume infusion at a rate of 12 mL/hr; resume infusion at normal infusion rate as tolerated
- infusion reaction, grade 4: discontinue the infusion and do not resume

Contraindications

- Specific contraindications have not been determined

Precautions

- Chronic obstructive pulmonary disease, moderate to severe (unapproved use); risk of grade 3 bronchospasm during infusion.
- Cytopenias, including prolonged severe neutropenia and thrombocytopenia may occur; monitoring recommended.
- Hepatitis B infection, carriers or at risk of infection; risk of hepatitis B reactivation with fulminant hepatitis, hepatic failure, and death; evaluate for

evidence of infection before beginning treatment and closely monitor for reactivation for 6 to 12 months following therapy; discontinue therapy if viral hepatitis occurs.

- Infusion reactions, some serious (eg. bronchospasm, dyspnea, laryngeal edema, pulmonary edema, angioedema, cardiac ischemia/infarction) have been reported; especially during first 2 infusions; premedication is recommended; depending on the severity of the reaction, adjustment in infusion rate, interruption, and/or discontinuation of therapy is recommended.
- Obstruction of small intestine may occur.
- Progressive multifocal leukoencephalopathy (PML) including fatalities, may occur; new onset or changes in preexisting neurological signs and symptoms may be indicative of PML; discontinue therapy if PML occurs.
- Viral vaccination, live; do not use in patients who recently received ofatumumab therapy.

Potential Side Effects

Common

- Dermatologic: rash (all grades, 14% to 17%; grade 3 or greater, less than 1% to 2%)
- Gastrointestinal: diarrhea (18% to 19%), nausea (11% to 12%)
- Hematologic: anemia (all grades, 16% to 17%; grade 3 or greater, 5% to 8%)
- Respiratory: bronchitis (all grades, 11% to 19%; grade 3 or greater, less than 1% to 2%), cough (19%), dyspnea (all grades, 14% to 19%; grade 3 or greater, 2% to 5%), pneumonia (all grades, 23% to 25%; grade 3 or greater, 14% to 15%), upper respiratory infection (3% to 11%)
- Other: fatigue (15%), Fever (all grades, 20% to 25%; grade 3 or greater, 3% to 5%)

Serious

- Gastrointestinal: bowel obstruction
- Hematologic: neutropenia, Grade 3 or greater (42%)
- Hepatic: relapsing type B viral hepatitis
- Immunologic: infectious disease (all grades, 70%; grade 3 or greater, 29%), sepsis (all grades, 8% to 10%; grade 3 or greater, 8% to 10%)
- Neurologic: progressive multifocal leukoencephalopathy
- Other: complication of infusion (first infusion, 44%; second infusion, 29%)

Disposition of Unused Drug

Upon termination of the study all unused materials provided by GSK shall be promptly returned at GSK's expense, or, at GSK's option, destroyed with the destruction certified in writing according to MDACC Institutional Drug Destruction Policy.

4.0 PATIENT ELIGIBILITY

4.1 Inclusion criteria:

1. Diagnosis of chronic lymphocytic leukemia (CLL) / small lymphocytic lymphoma (SLL), previously untreated, Rai stage 0-II
2. At least 1 of the following high-risk features for previously untreated patients:
 - Rai stage II disease
 - Rai stage 0-I with disease-related fatigue
 - Serum β 2M \geq 3 mg/L
 - Absolute lymphocyte count \geq 25,000/ μ L
 - Unmutated *IGHV* gene or *IGHV3-21*
 - ZAP70 positive (\geq 20% by flow cytometry or positive by immunohistochemistry)
 - CD38 positive (\geq 30% by flow cytometry)
 - Deletion 11q or 17p by FISH
3. ECOG PS \leq 2
4. Age \geq 18 years
5. Patients must have adequate renal and hepatic function (creatinine <2 mg/dL, total bilirubin <2 mg/dL). Patients with renal or liver dysfunction due to organ infiltration with CLL/SLL may be eligible after discussion with the study chairman
6. Provide informed consent
7. Female patients (including those <1 year post-menopausal) and male patients who have not undergone previous surgical sterilization must agree to use contraception.

4.2 Exclusion Criteria:

1. Presence of 2008 IWCLL/NCI-WG indication for CLL treatment:
 - Constitutional symptoms related to CLL/SLL:
 - Fever $> 100.5^{\circ}\text{F}$ for \geq 2 weeks or night sweats for > 1 mo, both without evidence of infection
 - Unintentional weight loss of $\geq 10\%$ body weight in previous 6 months
 - Extreme fatigue (ECOG PS > 2 ; inability to work or perform usual activities)
 - Lymphocyte doubling time of ≤ 6 months or 50% increase in absolute lymphocyte count within 2 months
 - Progressive anemia (Rai stage III) or thrombocytopenia (Rai stage IV)
 - Recurrent infections unrelated to hypogammaglobulinemia
 - Autoimmune phenomenon poorly responsive to corticosteroids or other standard therapy
 - Massive, progressive or symptomatic lymphadenopathy (> 10 cm in longest diameter) or splenomegaly (> 6 cm below left costal margin)
2. Prior or concurrent chemotherapy, radiotherapy, or immunotherapy for CLL

3. Active infection (febrile and requiring IV/PO antibiotics) including hepatitis C or HIV, or significant medical illness including renal, cardiac, pulmonary disease, or current active hepatic or biliary disease (with exception of patients with Gilbert's syndrome, asymptomatic gallstones, liver metastases or stable chronic liver disease per investigator assessment)
4. Positive serology for Hepatitis B virus (HB) defined as a positive test for HBsAg. In addition, if negative for HBsAg but HBcAb positive (regardless of HBsAb status), a HB DNA test will be performed and if positive the patient will be excluded.
 - A. Consult with a physician experienced in care and management of subjects with hepatitis B to manage/treat subjects who are anti-HB positive.
5. Pregnant or breast feeding females are not eligible

5.0 TREATMENT PLAN

This is a single-arm, open label, phase II trial of single-agent ofatumumab.

Patients will receive ofatumumab 300 mg dose 1, then 1000 mg weekly for 7 additional weekly doses (8 doses). All doses will be administered at MDACC. Allopurinol 300 mg PO daily for the first 7 days of course 1 is recommended for tumor lysis prophylaxis.

There are no required prophylactic antibiotics. Herpes virus and PCP prophylaxis may be given at the discretion of the treating physician but is recommended for patients with recent or concurrent corticosteroid use.

Growth factors (neutrophil, erythrocyte, platelet) may be used at the discretion of the treating physician, if clinically indicated.

Pre-medication for each ofatumumab infusion must be given within 30 minutes to 2 hours prior to the infusion:

Table 1. Pre-medication Requirements prior to Ofatumumab Infusions

Infusion #	Acetaminophen (po) or equivalent	Antihistamine (IV or po) diphenhydramine or equivalent	Glucocorticoid (IV) prednisolone or equivalent
1 st	1000 mg	50 mg	50 mg
2 nd	1000 mg	50 mg	50 mg
3 rd -N th	1000 mg	50 mg	0 – 50 mg ¹

1. If the 2nd infusion has been completed without the subject experiencing any grade = 3 AEs, pre-medication with corticosteroid may be reduced or omitted before the 3rd to Nth infusion at the discretion of the treating physician.

First Infusion of 300 mg ofatumumab

The first dose administered of ofatumumab will be 300 mg to minimize infusion reactions. The initial rate of the first infusion of **300 mg** ofatumumab (0.3mg/ml) should be 12mL/h. If no infusion reactions occur the infusion rate can be increased every 30 minutes, to a maximum of 200 mL/h, according to Table 2.

Table 2. Infusion rate at 1st Ofatumumab Infusion

Time	mL/hour
0 – 30 minutes	12
31 – 60 minutes	25
61 – 90 minutes	50
91 – 120 minutes	100
121 – 150+minutes	200

If an infusion reaction develops, the infusion should be temporarily slowed or interrupted. Upon restart, the infusion rate should be half of the infusion rate at the time the infusion was paused. If, however, the infusion rate was 12 mL/hour before the pause, the infusion should be restarted at 12 mL/hour. Hereafter, the infusion rate may be increased according to the judgment of the investigator, in the manner described in this section.

Subsequent infusion of full dose (1000 mg) ofatumumab

If the previous infusion was completed without grade ≥ 3 infusion-associated AEs, the subsequent infusion of the first full dose of ofatumumab can start at a rate of 25 mL/hour and can be doubled every 30 minutes up to a maximum of 400 mL/h, according to Table 3.

Duration of the infusion will be approximately 4 hours if this schedule is followed. If the previous infusion was completed with grade ≥ 3 infusion-associated AEs, the subsequent infusion should start at a rate of 12 mL/hour according to Table 3.

Table 3. Infusion rate at subsequent Ofatumumab Infusion

Time	mL/hour
0 – 30 minutes	25
31 – 60 minutes	50
61 – 90 minutes	100
91 – 120 minutes	200
121+ minutes	400

During infusion the patient should be monitored closely and appropriate measurements should be performed whenever judged necessary.

There are no proposed or planned ofatumumab dose reductions for toxicities. Toxicities will be addressed by escalating premedication, slowing the infusion rate or delaying planned dose as determined by the treating physician.

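### The treatment plan's restart rule after an infusion reaction ignores severity, has no stop for grade 4, and covers only the first of eight infusions

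*Combined protocol and SAP*

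**What the plan says.** Section 5.0, under the heading for the first 300 mg infusion, responds to a reaction of any grade in the same way: "If an infusion reaction develops, the infusion should be temporarily slowed or interrupted". The restart rate follows: "Upon restart, the infusion rate should be half of the infusion rate at the time the infusion was paused". The only exception is a floor: "If, however, the infusion rate was 12 mL/hour before the pause, the infusion should be restarted at 12 mL/hour". Later increases are left to the investigator's judgment.

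For the 1000 mg infusions, Section 5.0 gives Table 3 and one rule that depends on grade. If the previous infusion was completed with an infusion-associated event of grade 3 or higher, "the subsequent infusion should start at a rate of 12 mL/hour according to Table 3". That sets the start of the next infusion, not a restart within the same one. Section 5.0 closes with a general sentence: "Toxicities will be addressed by escalating premedication, slowing the infusion rate or delaying planned dose as determined by the treating physician".

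Section 3.0, Dose Adjustments, separates the grades:
- Grade 1 or 2: interrupt, then resume at half the previous rate if the reaction resolves or stays at grade 2 or below.
- Grade 3: "interrupt infusion and if reaction resolves or remains less than or equal to grade 2, resume infusion at a rate of 12 mL/hr".
- Grade 4: "infusion reaction, grade 4: discontinue the infusion and do not resume".

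**The concern.** Section 5.0 is what staff follow at the infusion chair, and it applies the mildest step in Section 3.0 (half rate) to every reaction. Three protections found in Section 3.0 are absent: the 12 mL/h restart after grade 3, the condition that the reaction has come down to grade 2 or lower, and the stop after grade 4. Section 5.0 does not refer to Section 3.0, which is background text whose dosing schedule is that of the refractory-disease regimen. For the seven 1000 mg infusions staff have no restart rate at all.

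Section 5.0 does treat severity as relevant, but only from one infusion to the next. A patient with a grade 3 reaction starts next week's infusion at 12 mL/h, yet today's infusion may restart well above that.

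Exclusion criterion 1 in Section 4.2 removes anyone who already needs treatment for CLL, so an avoidable acute risk is harder to justify here than in refractory disease.

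**Working it through.** **Inputs.** Section 5.0: first-infusion concentration 0.3 mg/mL, Table 2 (12, 25, 50, 100, 200 mL/h), Table 3 (25, 50, 100, 200, 400 mL/h), half-rate restart with the 12 mL/h floor. Section 3.0: prepared volume 1000 mL, graded restart rules. Section 2.0: 31 + 30 patients randomized in the trial of ofatumumab with fludarabine and cyclophosphamide (O-FC).

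**The plan's own figure.** Section 5.0 puts a 1000 mg infusion at about 4 hours. Under Table 3, the first 2 h deliver 0.5 × (25 + 50 + 100 + 200) = 187.5 mL. The remaining 812.5 mL at 400 mL/h takes 2.03 h, total 4.03 h. The figure reproduces, which supports reading the rates against a 1000 mL bag.

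**Grade 3 reaction in the first infusion.** Section 5.0 restart = half the paused rate (12 mL/h if paused at 12). Section 3.0 restart = 12 mL/h.

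| Rate at pause (mL/h) | Section 5.0 restart (mL/h) | Section 3.0 restart (mL/h) | Ratio |
|---|---|---|---|
| 12 | 12 | 12 | 1.0 |
| 25 | 12.5 | 12 | 12.5/12 = 1.04 |
| 50 | 25 | 12 | 25/12 = 2.1 |
| 100 | 50 | 12 | 50/12 = 4.2 |
| 200 | 100 | 12 | 100/12 = 8.3 |

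At 0.3 mg/mL the last row is 100 × 0.3 = 30 mg/h against 12 × 0.3 = 3.6 mg/h.

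**How much of the infusion runs at rates where the sections differ.** Volume: 300 mg / 0.3 mg/mL = 1000 mL. The first 2 h of Table 2 deliver 0.5 × (12 + 25 + 50 + 100) = 93.5 mL. The remaining 906.5 mL at 200 mL/h takes 4.53 h, total 6.53 h. Time at 50 mL/h or more is 6.53 − 1.0 = 5.53 h (85%); time at 200 mL/h is 4.53 h (69%). These are shares of time, not of risk: the documents do not say when reactions occur.

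**Grade 4.** Section 5.0 names no stop and its restart rule has no upper grade limit. Section 3.0 forbids resumption.

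**1000 mg infusions.** Section 5.0 gives no restart rate. If staff borrowed the first-infusion rule at 400 mL/h, they would restart at 200 mL/h, and 200/12 = 16.7 times the Section 3.0 rate for grade 3.

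**How often this could arise.** For the O-FC trial in previously untreated patients, Section 2.0 reports: "There were no ofatumumab infusion-related reactions" of grade 3 or higher. Taking all 61 randomized patients as treated, the one-sided 95% upper bound for 0/61 is 1 − 0.05^(1/61) = 4.8%. Applied to 44 patients this is 0.048 × 44 = 2.1. It is an upper bound, not an expected count, and it comes from combination therapy. Section 3.0 lists infusion complications at 44% for the first infusion and 29% for the second in its side-effect list, without giving grades.

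**Other places a rule might sit.** The toxicity stopping rule in Section 10.0 counts related grade 4 or higher events lasting more than a week; it governs the trial, not a single infusion. Section 9.0 lists progression, active HBV infection or hepatitis, and patient request. Neither supplies a restart or stop rule within an infusion.

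**The case against.** The strongest reply is that the graded rules are already in the protocol. The Dose Adjustments entries in Section 3.0 name no regimen, dose or infusion number, and where Section 5.0 is silent (grade 4, and restart in the 1000 mg infusions) it does not contradict them. On this view the only direct numerical conflict is the first-infusion restart after grade 3, and a cross-reference would cure the rest. In addition, the half-rate rule says how fast to restart, not that one must; patients are closely monitored, and toxicity handling is left to the treating physician.

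The 8.3-fold ratio also describes only the moment of restart. Section 3.0 lets the rate return to normal as tolerated. With doubling every 30 minutes (12, 24, 48, 96 mL/h) it would reach 96 mL/h after 90 minutes. And 30 mg/h is not far above the 24 mg/h at which Section 3.0 starts dose 2.

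Much of this stands as a limit on size. The ratio is a maximum, reaction timing is unknown, and severe reactions may be few. It does not remove the gap. Section 5.0 contains no pointer to Section 3.0, its wording for the first infusion presumes that the interruption is temporary, and physician discretion is not a stop rule. Its list of responses to toxicity omits discontinuation. Nothing in the protocol explains why a severe reaction should be handled less cautiously here than in its own drug information.

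**Conclusion.** The concern holds. Section 5.0 sets one restart rate for first-infusion reactions of every grade, has no condition on resolution and no stop after grade 4, and gives no restart rule for the seven 1000 mg infusions. For a grade 3 reaction the two sections differ materially only from 50 mL/h upward: 2.1-fold at 50, 4.2-fold at 100 and at most 8.3-fold at 200 mL/h. These ratios follow from the stated rates alone; the time shares also assume an uninterrupted Table 2 infusion of 1000 mL. How many patients would be affected cannot be fixed from the documents; the O-FC bound of about 2 in 44 is only indicative.

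This is a safety wording gap that should be corrected. It affects no endpoint, sample size, stopping boundary or analysis.

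**What to change.** State the rules by grade in Section 5.0 and apply them to all eight infusions:
- Grade 1 or 2: interrupt or slow; resume at half the previous rate, with a minimum of 12 mL/h.
- Grade 3: interrupt; resume at 12 mL/h, and only once the reaction is grade 2 or lower.
- Grade 4: discontinue the infusion and do not resume it.

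Add discontinuation of the infusion to the general toxicity-handling sentence at the end of Section 5.0. Later rate increases as tolerated can stay as they are.

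The cost is a few sentences. No procedures are added, and the sample size, the analysis and Section 9.0 are unchanged. Whether a patient with a grade 4 reaction should be given the next weekly dose is a separate clinical decision that this wording does not settle; the sponsor may wish to address it in the same amendment.
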